In addition to the 2 planned interim efficacy analyses, the DMC will convene to review interim safety analysis results periodically.

The Lan-DeMets approach with O'Brien-Fleming type alpha spending function will be used for the first and second interim analyses and final analysis for OS. The stopping boundaries at each analysis time are provided in [Table 17](#).

Table 17. Stopping Boundaries for Efficacy Superiority Analyses

Planned Analyses	Efficacy Analysis	Events (%)	Stopping Boundary	
			HR ^a	Two-sided p-value
first IA	CR	-	-	0.03
If the test of CR is rejected in first IA	first IA	OS 158 (43%)	0.600	0.0013 ^b
	second IA	OS 257 (71%)	0.738	0.0148 ^b
	Final Analysis	OS 364 (100%)	0.811	0.0453 ^b
If the test of CR fails to be rejected in first IA	first IA	OS 158 (43%)	0.552	0.0002 ^b
	second IA	OS 257 (71%)	0.700	0.0043 ^b
	Final Analysis	OS 364 (100%)	0.781	0.0186 ^b

HR = hazard ratio, IA = interim analysis, OS = overall survival, CR = complete remission

a HR presented in the table is the 1-sided (lower) efficacy boundary.

b The boundary p-values at each analysis timepoint will be based on the actual observed events and adjusted by using the Lan-DeMets approach with O'Brien-Fleming type alpha spending function.

The primary efficacy endpoint of OS will be tested for superiority first at the significance level specified in [Table 17](#). If the superiority of OS is established, key secondary efficacy endpoints listed in [Table 18](#) will be tested for superiority. To strongly control the overall type I error across the testing of the primary and key secondary efficacy endpoints, a hierarchical testing strategy will be performed with a predefined order as listed below. For each key secondary endpoint, an O'Brien-Fleming boundary will be derived based on the information fraction at each interim analysis and the remaining type I error respectively per [Table 18](#).

Table 18. Definition of Information Fraction for Key Secondary Endpoints

Endpoint	Information Fraction at the First and Second Interim Analysis
ORR	Proportion of participants who have at least 8 months follow-up since randomization (including participants who have early discontinued, are lost to follow-up, or have died)
RBC transfusion independence rate	Proportion of participants who have at least 8 months follow-up since randomization (including participants who have early discontinued, are lost to follow-up, or have died)

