8.5. Efficacy Analysis

8.5.1. Analysis of Primary Efficacy Endpoints

The primary efficacy endpoints are CR rate as assessed by Investigators and OS. The analysis of CR rate will be conducted on the first 348 randomized participants in the ITT Analysis Set. The analysis of OS will be conducted on the ITT Analysis Set.

The difference in CR rates between the 2 arms will be tested using the Cochran-Mantel-Haenszel test, stratified by the randomization stratification factors including region, baseline cytogenetic risk, and bone marrow blast percentage. The point estimate of the CR rate and the corresponding 2-sided exact 95% CI based on Clopper-Pearson method will be provided for each treatment arm.

Log-rank test, stratified by the randomization stratification factors including region, baseline cytogenetic risk, and bone marrow blast percentage, is the primary analysis comparing treatment differences in OS. A stratified Cox regression model will be used to estimate HR and its 2-sided 95% CI. In addition, the KM method will be used to estimate median OS with its 95% CI, and the KM plots may also be provided.

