2. TYPE OF PLANNED ANALYSIS

2.1. DMC Interim Analyses

An external multidisciplinary data monitoring committee (DMC) reviewed the progress of the study, performed interim reviews of safety data at regular intervals, and provided recommendation to Gilead on whether the nature, frequency, and severity of AEs associated with study treatment warrant the early termination (ET) of the study in the best interests of the patient, whether the study should continue as planned, or whether the study should continue with modifications.

In addition, the DMC has reviewed the results from the 1st planned interim efficacy analysis and will review the results from the 2nd planned interim efficacy analysis. Based on the pre-specified superiority and futility rules, the DMC may make recommendations to Gilead on whether the study should be stopped early due to overwhelming efficacy, be terminated for futility, or continue as planned. Efficacy superiority boundaries are specified in Table 2-1 and non-binding futility rules are specified in Table 2-2.

The DMC's specific activities were defined by a mutually agreed unpon charter, which defined the DMC's membership, conduct, and meeting schedule.

While the DMC will be asked to advise Gilead regarding future conduct of the study, including possible early study termination, the ultimate decision on whether to implement or act based upon the recommendations of the DMC will be made by Gilead.

The study protocol specified 2 interim efficacy analyses conducted and evaluated by the DMC.

The first DMC interim efficacy analysis was conducted at 8 months after 348 patients had been randomized (data cut date: 12Aug2022). At that time, 144 deaths (39.6% of 364 deaths) were observed.

The second planned interim efficacy analysis will be conducted when approximately 257 deaths (71% of 364 deaths) have occurred, outstanding data queries have been resolved or adjudicated as unresolvable, and the data have been cleaned and finalized. In the case that the null hypothesis on CR rate was not rejected based on the first 348 randomized patients in the first interim analysis at a 2-sided significance level of 0.03, a non-binding futility analysis with a futility boundary of HR = 0.95 will be performed at the second planned interim analysis.

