- If the null hypothesis on CR based on the first 348 randomized patients was rejected in the first interim analysis at a 2-sided significance level of 0.03, $\alpha = 0.05$ (2-sided) will be allocated to the analysis of OS and key secondary endpoints in the first interim, second interim, and final analyses
- If the null hypothesis on CR rate based on the first 348 randomized patients was not rejected in the first interim analysis at a 2-sided significance level of 0.03, $\alpha = 0.02$ (2-sided) will be allocated to the analysis of OS and key secondary endpoints in the first interim, second interim, and final analyses

The Lan-DeMets approach with O'Brien-Fleming type alpha spending function are used for the first and second interim analyses, and final analysis for OS. The stopping boundaries at each analysis time are provided in Table 2-1.

		Efficacy		Stopping Boundary	
Planned Analyses		Analysis Events (%)		HRª	Two-sided p-value
First IA	λ	CR	-	-	0.03
	First IA	OS	144 ^b (40%)	0.570	0.000732
If the test of CR is rejected in	Second IA	OS	257 (71%)	0.738	0.0150*
first IA	Final Analysis	OS	364 (100%)	0.811	0.0453*
	First IA	OS	144 (40%)	0.519	0.000084
If the test of CR fails to be rejected in first IA	Second IA	OS	257 (71%)	0.700	0.0043*
	Final Analysis	OS	364 (100%)	0.781	0.0186*

 Table 2-1.
 Stopping Boundaries for Efficacy Superiority Analyses

HR = hazard ratio, IA = interim analysis, OS = overall survival, CR = complete remission

a HR presented in the table is 1-sided (lower) efficacy boundary.

b 144 deaths were observed at first interim efficacy analysis (data cut date: 12Aug2022).

* The boundary p-values at each analysis timepoint will be based on the actual observed events and adjusted by using the Lan DeMets approach with O'Brien-Fleming type alpha spending function.

Table 2-2.Non-Binding Futility Boundaries

			Non-Binding Futility Boundary
Planned Analyses		Efficacy Analysis	HR
If the test of CR fails to	First IA	OS	0.99
be rejected in first IA	Second IA	OS	0.95

HR = hazard ratio, IA = interim analysis, OS = overall survival

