2.2. Optional Interim Analysis Performed by Sponsor

At the time of the second interim efficacy analysis, if the efficacy superiority boundary of OS has been crossed, the Sponsor study team may be unblinded for the entire ITT Analysis Set by the data cutoff date and will conduct the efficacy and safety analyses. Gilead Oversight Committee will make the decision on whether study team will be unblinded.

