6.1.2. Statistical Hypothesis for the Primary Efficacy Endpoints

The first primary efficacy hypothesis was tested on CR rate difference between magrolimab + azacitidine (experimental arm) and placebo + azacitidine (control arm) based on the first 348 randomized patients at the 1st planned interim efficacy analysis. Using CR rate_{exp} and CR rate_{ctrl} to denote the CR rates for the experimental arm and control arm, respectively, the statistical hypotheses tested in this study is:

 H_0 : CR rate_{exp} = CR rate_{ctrl}

 H_1 : CR rate_{exp} \neq CR rate_{ctrl} (experimental arm is not equal to control arm in terms of CR rate)

The second primary efficacy hypothesis to be tested is that there is no difference between magrolimab + azacitidine (experimental arm) and placebo + azacitidine (control arm) in OS for patients. Using $S_{exp}(t)$ and $S_{ctrl}(t)$ to denote the OS distribution functions of the experimental arm and control arm, respectively, the statistical hypotheses to be tested in this study will be:

 $H_0: S_{exp}(t) = S_{ctrl}(t)$ at all time points t

 $H_1: S_{exp}(t) \neq S_{ctrl}(t)$ (experimental arm is not equal to control arm in terms of OS for some t > 0)

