6.1.3. Analysis of the Primary Efficacy Endpoints

The primary analysis of CR rates was done at the 1st interim efficacy analysis (data cut date: 12Aug2022) based on the first 348 randomized patients in the ITT Analysis Set using the Cochran-Mantel-Haenszel (CMH) test, stratified by the stratification factors at randomization. The odds ratio comparing the 2 arms adjusted for the stratification factors was presented along with 95% confidence interval (CI).

The point estimate of the CR rate and the corresponding 2-sided exact 95% CI based on the Clopper-Pearson method was provided for each arm. Patients, who are randomized but have no on-study response assessment or receive any new anticancer therapy including SCT prior to achieving CR, are considered as non-responders.

If the CR rate of experimental arm is higher than that of control arm and 2-sided p-value from the stratified CMH test using SAS procedure freq is less than 0.03, the null hypothesis of CR rate in Section 6.1.2 would be rejected and the superiority of experimental arm to control arm in terms of CR rate is established.

The primary analysis of OS will compare the OS distributions of two treatment groups using the stratified log-rank test, stratified by the stratification factors at randomization for the ITT Analysis Set. Medians, Q1, Q3 of the OS distributions, and the proportion of patients who are alive at 6, 12, 18 and 24 months from randomization will be estimated along with corresponding 95% CIs using the Kaplan-Meier method. Kaplan-Meier curves will be provided by treatment group.

If the median survival time of experimental arm is longer than that of control arm and two-sided p-value from the stratified log-rank test using SAS procedure Lifetest is less than the cutoff p-values based on observed number of OS events by the data cutoff date as mentioned in Section 2.1, the null hypothesis of OS in Section 6.1.2 will be rejected and the superiority of experimental arm to control arm in terms of OS is established.

In addition, the HR between the 2 treatment groups and its 95% CI will be estimated using the Cox proportional hazards regression model stratified by the stratification factors. For pre-specified non-binding futility analysis boundary of HR=0.95 at the second interim analysis if CR was not statistically significant, the HR from the Cox model will be used to check whether the futility boundary has been crossed or not.

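### SAP 6.1.3 takes the direction of the OS test from the Kaplan-Meier medians instead of the hazard ratio, so a result that crosses the Table 2-1 boundary can still be declared not superior

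*SAP*

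**What the plan says.** - **Decision rule, SAP 6.1.3.** The OS null is rejected and superiority established under a joint condition: "If the median survival time of experimental arm is longer than that of control arm and two-sided p-value from the stratified log-rank test" must lie below the cutoff for the observed number of deaths. The Cox HR is estimated in addition.
- **Hypotheses, SAP 6.1.2.** These concern whole survival curves. The alternative is that the "experimental arm is not equal to control arm in terms of OS for some t > 0".
- **Boundaries, SAP 2.1.** "Efficacy superiority boundaries are specified in Table 2-1 and non-binding futility rules are specified in Table 2-2". Each OS row of Table 2-1 gives a p-value and an HR, and a footnote says "HR presented in the table is 1-sided (lower) efficacy boundary". Table 17 of Protocol 8.3.1 carries the same note: "HR presented in the table is the 1-sided (lower) efficacy boundary".
- **Action on crossing, SAP 2.2.** At the second interim, "if the efficacy superiority boundary of OS has been crossed, the Sponsor study team may be unblinded". No median is mentioned.
- **Futility, SAP 6.1.3.** "the HR from the Cox model will be used to check whether the futility boundary has been crossed or not".
- **Protocol 8.5.1.** The stratified log-rank test "is the primary analysis comparing treatment differences in OS", with no condition on medians.

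Two further passages bear on the point. The sample-size text (Protocol 8.1 and SAP 1.3) words the OS null as equality of medians, which may be where the clause came from. SAP Section 10 reports no departures from the protocol's analyses.

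**The concern.** The log-rank test weighs deaths over the whole of follow-up, whereas the median reads the curves at one height. The two can point in different directions when hazards are not proportional. If the log-rank result favours magrolimab but its median is not longer, Table 2-1 is crossed and SAP 6.1.3 says superiority is not established. Two readers could then draw opposite conclusions on a primary endpoint from the same data. All the key secondary tests depend on the answer, because Protocol 8.5.2 allows none of them unless the OS null is rejected.

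There are two lesser problems. Neither document says how to apply the clause when a median has not been reached. And read by itself, SAP 6.1.3 does not rule out a significant log-rank result that favours control but comes with a longer experimental median. The HR column of Table 2-1 does rule that out, so this last point is only an inconsistency between the two rules.

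**Working it through.** **1. The plan's own figures reproduce.** Inputs from SAP 1.3 and 2.1: 364 deaths, medians 18 and 25.4 months, so HR = 18/25.4 = 0.7087.

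- Single-look power: expected z = |ln 0.7087| × √364 / 2 = 0.3443 × 9.539 = 3.285. Then Φ(3.285 − 1.960) = 90.7% at alpha 0.05, and Φ(3.285 − 2.326) = 83.1% at alpha 0.02. Group-sequential power is 90.3% and 82.7%. The plan states 90% and at least 80%.
- Boundary HR = exp(−2z/√deaths). For final p 0.0453, z = 2.002, and exp(−2 × 2.002/19.08) = 0.811. All six HR and p-value pairs in Table 2-1 reproduce.

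The boundaries follow from the log-rank statistic alone.

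**2. Simulation of the whole design.** 520 patients 1:1; exponential control survival, median 18 months; 1% annual loss; accrual ramping up to 520 patients at month 22; looks at 144, 257 and 364 deaths with the Table 2-1 p-values; unstratified log-rank; 10,000 trials per scenario. An unreached experimental median with a reached control median is counted as longer. The documents do not say which alpha branch applies, so both are shown.

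Planned effect, direction from HR < 1 versus median clause added: 90.1% and 90.1% (alpha 0.05); 82.3% and 82.3% (alpha 0.02). Favourable rejections under the null: 2.68% and 2.68%; 1.03% and 1.03%.

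Delayed effect (assumed: no difference until the stated month, then the stated HR):

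| Delay / later HR | Alpha 0.05: HR direction | Alpha 0.05: median clause | Loss (points) | Alpha 0.02 loss: futility ignored / followed (points) |
|---|---|---|---|---|
| 3 mo / 0.65, 6 mo / 0.6, 9 mo / 0.5 | – | – | ≤ 0.03 | – |
| 12 mo / 0.5 | 85.4% | 84.7% | 0.7 | 0.2 / 0.01 |
| 15 mo / 0.5 | 66.0% | 63.5% | 2.5 | 0.9 / 0.2 |
| 18 mo / 0.5 | 45.7% | 40.4% | 5.2 | 1.8 / 0.6 |
| 18 mo / 0.4 | 65.7% | 51.2% | 14.5 | 7.6 / 1.8 |

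Losses are computed before rounding. With uniform accrual (4,000 trials) the alpha 0.05 losses are 0.75, 2.6, 5.2 and 15.2 points.

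**3. Hand check of the 18-month, HR 0.5 row.** Both arms have lost about half their patients by month 18, roughly 260 deaths, so about 364 − 260 = 104 of the final deaths come after separation. Expected z ≈ 0.693 × (104/364) × √364/2 = 1.89. Power at the final look ≈ Φ(1.89 − 2.00), about 45%, in line with the simulated 45.7%.

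**4. The two rules do conflict in the lost trials.** In the 12- to 18-month scenarios every lost trial was discordant at the final look. At alpha 0.05 there were 69, 250, 524 and 1,451 of them per 10,000, and all had a Cox HR at or below 0.811. Each met both columns of Table 2-1 and failed SAP 6.1.3.

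**5. Unreached medians.** At the planned effect, the experimental median is unreached in roughly 4% to 9% of significant results at the 257-death look, depending on accrual pattern and alpha branch. No delayed effect is needed for this.

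**6. Result favouring control.** With crossing hazards at month 18 (assumed: HR 0.8 then 2.0, or 1.0 then 1.8), SAP 6.1.3 read alone would label 2.9% or 2.3% of trials superior at alpha 0.05. With the Table 2-1 HR column applied, the figure is 0.

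**The case against.** The clause can only remove favourable rejections, so it is conservative, and it leaves the stated power alone. The losses need 12 months or more of no effect, followed by a strong one, with separation near the control median. The documents offer little support for that. The remark on delayed benefit in Protocol 5.7.1 concerns treating until progression is confirmed, not survival curves. The Max-Combo test in SAP 6.1.6 is optional and exploratory. Time to response in the earlier study was 1.9 months (Protocol 2.1.5.3). With an 18-month delay and HR 0.5, power is already below 50% whichever direction rule is used. The sample-size text does speak of medians, so a sponsor could intend both conditions. SAP 2.2 only permits unblinding, at an oversight committee's decision, and does not itself declare superiority.

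Most of this stands and limits the point to a minor one. It does not remove it. If the median condition is a deliberate extra hurdle, it is missing from the protocol's OS analysis and from Table 2-1, and SAP Section 10 does not declare it. The equal-medians wording belongs to a power statement; under the proportional-hazards planning model it amounts to the hypothesis on curves, but outside that model it does not. Nor does the objection deal with an unreached median, which can arise under the plan's own assumptions.

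**Conclusion.** The concern holds, as a minor one. SAP 6.1.3 adds a direction condition based on a different summary from the one tested, and it can contradict Table 2-1. The clause has no measurable effect at the planned HR, if an unreached experimental median is read as longer. It costs at most 0.03 points for the delays of 9 months or less examined. At alpha 0.05 it costs 0.7 to 5.2 points for delays of 12 to 18 months followed by HR 0.5, and 14.5 points for 18 months followed by HR 0.4. In the alpha 0.02 branch the losses for these four scenarios are 0.2 to 7.6 points, or 0.01 to 1.8 if the non-binding futility rule is followed. The delays and later hazard ratios are assumptions. The simulations are unstratified, whereas the planned test is stratified.

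**What to change.** Replace the median clause in SAP 6.1.3 with wording such as: *If the stratified Cox HR (experimental versus control) is below 1, that is, the stratified log-rank statistic favours the experimental arm, and the two-sided stratified log-rank p-value is below the Section 2.1 boundary, the OS null hypothesis is rejected and superiority of the experimental arm is established.* Report the Kaplan-Meier medians descriptively.

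This matches Table 2-1, SAP 2.2 and Protocol 8.5.1, and an unreached median no longer matters to the decision. The boundaries, alpha allocation, futility rule and stated power do not change, and no further data or patients are needed. The edit should be made before the second-interim data are finalised, because a later change to a primary decision rule would look data-driven.

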6.1.4. Follow-up Time

The follow-up time for OS is defined as the interval from date of randomization to the death date for patients who died on or prior to the data cutoff, or from the date of randomization to the last known alive date for patients who are alive up to the data cutoff. The follow-up time will be summarized by treatment groups using descriptive statistics including median and range (minimum and maximum). It will also be summarized by treatment groups using statistics such as median, Q1, Q3 with corresponding 95% CIs estimated with the reverse Kaplan-Meier (K-M) method. The reverse K-M model switches the event/censoring indicators of patients in the original OS analysis with Kaplan-Meier method. It considers patients lost to follow-up or administratively censored due to analysis data cut as achieving the full follow up, and the full follow up time of those patients who died could not be observed as it is 'censored' by death.

6.1.5. Sensitivity Analysis of the Primary Efficacy Endpoint

To assess the robustness of the primary CR results, the following sensitivity analysis will be performed at the second interim and final analysis:

• CR will be analyzed based on all randomized patients who have at least 8 months follow-up since randomization in the ITT Analysis Set for the Cochran-Mantel-Haenszel (CMH) test.

To assess the robustness of the primary OS results, the following sensitivity analysis will be performed:

• OS will be analyzed using the stratified log-rank test, stratified by the stratification factors in IXRS. In addition, the HR between the 2 treatment groups and its 95% CI will be estimated using the Cox proportional hazards regression model stratified by the stratification factors in IXRS.

6.1.6. Exploratory Analysis of the Primary Efficacy Endpoint

An exploratory analysis may be performed to investigate the potential prognostic factors influencing the primary efficacy endpoint OS using the Cox regression model approach. The variables with prognostic potential will be included in the model as covariates to identify plausible significant factors on OS, such as age, gender, percentage of bone marrow blast, ECOG, etc. In addition, the Max-Combo test may be performed to compare the OS distributions of two treatment groups.

6.2. Secondary Efficacy Endpoints

6.2.1. Definition of Secondary Efficacy Endpoints

Duration of CR: The DCR is measured from the time measurement criteria are first met for CR to the first date of relapse, disease progression or death, whichever occurs earlier. Those who are not observed to relapse, disease progression or die will be censored at their last response assessment date with evidence of no relapse/no disease progression. Patients who achieve a CR and then proceed to SCT will continue to be followed for the response assessment posttransplant, will be included in the analysis of DCR, and will not be censored at the time of transplant. If patients start taking new anticancer therapies (excluding SCT) before relapse, disease progression or death, DCR will be censored at the last response assessment on or before the initiation of the new anticancer therapies.

Objective Response Rate (ORR): The ORR is the proportion of patients who reach objective response including CR, PR, marrow CR, or hematologic improvement per IWG 2006 MDS criteria on or prior to initiation of any new anticancer therapy, including SCT.

Duration of Response (DOR): The DOR is measured from the time measurement criteria are first met for objective response to the first date of relapse, disease progression after the initial objective response or death, whichever occurs earlier. Those who are not observed to relapse, disease progress after the initial objective response or die will be censored at their last response assessment date with evidence of no relapse/no disease progression. Patients who achieve a response and then proceed to SCT will continue to be followed for the DOR posttransplant, will be included in the analysis of DOR, and will not be censored at the time of transplant. If patients start taking new anticancer therapies (excluding SCT) before relapse, disease progression or death, DOR will be censored at the last response assessment on or before the initiation of the new anticancer therapies.

RBC Transfusion Independence Rate: The RBC transfusion independence rate is the proportion of patients who have a 56-day or longer period with no RBC transfusions at any time between randomization and initiation of any new anticancer therapy, including SCT, among all patients who are RBC transfusion-dependent at baseline.

Event-free Survival: The EFS is defined as the time from randomization to transformation to AML or death from any cause, whichever occurs first. Transformation assessments and deaths post SCT will be included in the analysis. Patients who are not observed to have one of these events during the study will be censored at their last response assessment date with evidence of no transformation to AML. If patients start taking new anticancer therapies (excluding SCT) before transformation to AML or death, EFS will be censored at the last response assessment on or before the initiation of the new anticancer therapies. Patients will be censored at the date of randomization if no response assessment performed after randomization and the patients didn't die.

CR in TP53 Mutant Population: CR in TP53 Mutant Population is defined as the proportion of patients who achieve a morphologic CR based on Investigator assessments using IWG criteria {Cheson 2006} on or prior to initiation of any new anticancer therapy, including SCT in TP53 mutant population.

MRD-negative Response Rate: The MRD-negative response rate is defined as the proportion of patients who achieve a morphologic CR or marrow CR based on Investigator assessments using IWG criteria {Cheson 2006} and reach MRD-negative disease status on or prior to initiation of any new anticancer therapy, including SCT. MRD-negative disease status will be assessed using a multiparameter flow cytometry-based assay performed by a central laboratory.

Time to Transformation to AML: Time to transformation to AML is defined as the time from randomization to transformation to AML. Patients who are not observed to have transformation to AML will be censored at their last response assessment date with evidence of no AML diagnosis. Transformation assessments post SCT will be included in the analysis. If patients start taking new anticancer therapies (excluding SCT) before documented AML diagnosis, Time to Transformation to AML will be censored at the last response assessment on or before the initiation of the new anticancer therapies. Patients will be censored at the date of randomization if no response assessment performed after randomization.

Progression-free Survival: PFS is defined as the time from randomization to the date of documented disease progression (including treatment failure by IWG criteria or relapse after PR/CR), or death from any cause, whichever occurs first. Response assessments and deaths post SCT will be included in the analysis. Those who are not observed to have one of these events will be censored at their last response assessment date with evidence of no disease progression/relapse. If patients start taking new anticancer therapies (excluding SCT) before disease progression (including treatment failure by IWG criteria or relapse after PR/CR) or death, PFS will be censored at the last response assessment on or before the initiation of the new anticancer therapies. Patients will be censored at the date of randomization if no response assessment performed after randomization and the patients didn't die.

FACT-Anemia Response Rate: The FACT-Anemia response rate is defined as the proportion of patients who showed clinically meaningful improvement in health-related quality of life (HRQoL) based on the score from the FACT-Anemia instrument on or prior to initiation of any new anticancer therapy, including SCT {Cella 2002}. The minimal clinically meaningful difference of 7.0 as suggested in the referenced literature will be used as cutoff for clinically meaningful improvement. Patients, who are randomized but have no baseline or no postbaseline FACT-Anemia questionnaire assessment or receive any new anticancer therapy including SCT prior to achieving the FACT-Anemia response, will be considered as non-responders.

